Participant Recruitment: A maximum number of 120 eligible patients **will be** enrolled (with goal 100 completed) and randomized from Sea Mar health centers. The study will recruit from 6 primary care clinics (Des Moines Medical Clinic, White Center Medical Clinic, Federal Way Medical Clinic, Kent Medical Clinic, Seattle Medical Clinic, Burien Medical Clinic) given the high volume of Latinx populations who receive care at these sites. Additional participants may come from other Sea Mar clinics, and from community engagement or the University of Washington clinics. Patients will be referred by their local primary care providers or by Sea Mar health education team and their review of patients with uncontrolled diabetes or new diagnosis of diabetes in the Sea Mar health system record. Patients who express interest will be contacted by telephone, email and/or in person by on-site research coordinators to ascertain interest and confirm eligibility criteria. Eligible individuals will be scheduled for their screening visit, ideally within 2 weeks of the contact.

Recruitment will be quarterly with one Spanish and one English speaking 12-week curriculum with a goal of 20-35 participants per DSMES cycle. We anticipate a roughly even distribution between English and Spanish speaking participants (e.g., 10-20 participants per cohort per language-specific curriculum cycle). A total of 4-6 DSMES cycles will need to be completed to reach 100 participants.

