The study screening and research procedures will take place at the patient's home or in the health education office, or another Sea mar Clinic location, per patient preference. If possible, the visit will be performed in person, but given the increase in tele-health visits during the COVID pandemic, if a potential participant is unable to complete the screening visit and/or research visits in person, then tele-visits for the research visits will be offered.

Population:

We propose to perform an observational prospective study that will involve 100 subjects with confirmed type 2 Diabetes. There will be 50 participants in the RT-CGM+education intervention group and 50 in blinded-CGM+education group. Patients with type 1 diabetes as well as controlled diabetes <8.0 % will be excluded (8.0 or greater included). Sea Mar clinics care for more than 8,500 patients living with diabetes, and when the designated clinics were reviewed for Latinx patients with A1C ≥8.0%, over 460 potential participants were found. Thus, we will have a robust population for recruitment and diabetes self-empowerment. Additionally, participants may be found in the local community or UW clinics

E. Statistical Considerations

Sample Size Estimation

In this study, we plan to enroll and include a total of n=100 study participants. The study is designed and sized first for assessing the primary endpoint of change in A1C from baseline to 12 weeks (Aim 1), and secondarily to assess the impact of RT-CGM on A1C. To assess statistical power, we assumed a standard deviation in baseline A1C of 1.2 and a reduced standard deviation of 1.0 at 12 weeks to reflect an anticipated reduction in A1C due to the *Compañeros en Salud* curriculum. We further assume a correlation in A1C measurements of $r=0.5$, which is likely to be higher and will result in greater statistical power. Finally, assuming a 15% reduction in the effect sample size (n=85) due to attrition, the study is sized to detect reductions in A1C of 0.4 or larger with 90% statistical power. If the actual correlation between baseline and week 12 HbA1c measurements is $r=0.7$ or higher, the study has 90% power to detect differences in A1C as small as 0.3. Under similar assumptions, the study is sized to detect a 0.6 difference in 12-week HbA1c between subjects randomized to RT-CGM vs blinded CGM (power = 0.82 assuming $r=0.5$; power=0.93 assuming $r=0.7$). A two-sided type 1 error rate of 0.05 was assumed throughout.

Data Analysis Plan

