AIM 1: Our primary endpoint for Aim 1 is the change in A1C from baseline to 12+/-2 weeks (end of the intervention period). Secondary outcomes include between-group differences in change in A1C at

24+/-2 weeks and changes in body weight, BMI, and blood pressure at 12+/-2 and 24+/-2 weeks. We will use simple descriptive statistics to quantify between-group differences in changes in CGM indices including TIR, mean glucose, mean amplitude of glycemic excursions, TAR, TBR, and coefficient of variation. The primary outcome of A1C will be assessed using a random-intercept random-slope linear mixed effects regression model that adjusts for an indicator of RT-CGM and time (baseline, visit 2, and visit 3) as fixed effects. To assess the effectiveness of the *Compañeros en Salud* curriculum, inference for Aim 1 will focus on the change in A1C from baseline to 12 weeks for the entire cohort (regardless of RT-CGM status). Secondary outcome measures of TIR, body mass index, waist circumference, and systolic/diastolic blood pressure will be similarly assessed using a generalized linear mixed effects model appropriate for each type of outcome measurement.

We will conduct a missing data analysis to describe and characterize enrolled participants who do not provide data due to attrition. Linear mixed effects models naturally handle intermittent missing data through maximum likelihood estimation. As described by Molenberghs and Kenward,⁴⁹ we will use inverse probability weighting in secondary analysis within each longitudinal regression model to inflate the weights of cases that are underrepresented in the analysis due to selective attrition and/or non-participation. We will also conduct sensitivity analyses using 10-fold multiple imputation to assess the robustness of the results when missing data are imputed. The characteristics of non-responders will be summarized in our final report, and we will present the sensitivity of the estimated treatment effect due to alternative missing data methods

Aim 2: For this Aim, the primary outcome will be the difference in % of DSMES education sessions attended for participants who complete the study before and after the stakeholder convening. Additional endpoints will similarly assess the differences in the following metrics of participant engagement: % adherence to RT-CGM use, % of participants who complete all study visits, and % of eligible patients who enroll in the study.

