N: Glucose/CGM Data /Evaluation Measures: For participants in both the education-only and RT-CGM study arms, the % time the CGM device was worn over each period of use will be captured. Glycemic outcome measures include time in range (TIR), mean glucose, coefficient of variation, mean amplitude of glucose excursion (MAGE), % time below range (TBR) (<70 mg/dL), and % time above range (TAR) (>180 mg/dL). Between-group comparisons for CGM-derived glycemic metrics will be assessed based on changes from baseline to study week 12 and baseline to study week 24.

O. Advisory Board: We will convene key stakeholders in an advisory board after approximately 20-25% of participants have completed the 12-week intervention and again during years 2 and 3 of the study. The first convening will occur after 1 education cycle has been completed for both an English- and Spanish-speaking cohort, with an estimated 20-30 participants having undergone the intervention. Key stakeholders will meet specifically to address barriers to entering and completing the education intervention, implementing the behavioral changes recommended by the DSMES curriculum, and adhering to CGM use in the RT-CGM arm of the study. Accordingly, invited stakeholders will include patients who were eligible but opted against participation, participants who enrolled but did not complete the intervention phase of the study, participants who completed the 12-week intervention, and participant's household member if desires. Additional stakeholders are described below. The board will be asked to assess possible barriers to participant engagement, including the following: support for technology use, adequacy of RT-CGM training, food insecurity, safety concerns, and time commitment and sustainability.

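### The primary pooled A1C change takes no account of class membership, so its standard error is too small if there is any positive within-class correlation; the size depends on an ICC the plan does not give.

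*Combined protocol and SAP*

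**What the plan says.** Section E, Data Analysis Plan, Aim 1, makes the pooled pre-post change the primary inference: "inference for Aim 1 will focus on the change in A1C from baseline to 12 weeks for the entire cohort", regardless of RT-CGM status. The model is a "random-intercept random-slope linear mixed effects regression model that adjusts for an indicator of RT-CGM and time (baseline, visit 2, and visit 3"). No class, cycle or facilitator term, cluster-robust standard error or ICC is mentioned. A language indicator is added only in the Aim 3 models.

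Section E, Sample Size Estimation, sizes the study first for this change. It gives the inputs as follows: "we assumed a standard deviation in baseline A1C of 1.2 and a reduced standard deviation of 1.0 at 12 weeks"; "We further assume a correlation in A1C measurements of $r=0.5$, which is likely to be higher"; "assuming a 15% reduction in the effect sample size (n=85) due to attrition"; and "A two-sided type 1 error rate of 0.05 was assumed throughout". From these it claims 90% power for a 0.4 reduction. No design effect is applied.

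Section D has one Spanish and one English curriculum per cycle, expects 4-6 cycles, and anticipates "10-20 participants per cohort per language-specific curriculum cycle". Section G describes group classes with discussion, role-play and shared review of goals. Section O adds that the study will be revised after stakeholder input, so later cycles may differ from the first.

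**The concern.** People in the same class share discussion, a language and a calendar period. Their A1C changes may therefore be correlated. In the RT-CGM comparison this matters little: participants are randomised individually and classes are split by language, not by arm, so a class effect common to both arms largely cancels. In the pooled change nothing cancels, and a class effect on change goes straight into the estimated mean.

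A random intercept and slope for each participant cannot absorb this, because the model still treats the slopes of different people as independent. That these random effects are at participant level is the natural reading of the plan, though it is not spelled out. At stake are the type I error and interval width of the contrast the plan calls primary and, second, the stated power.

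**Working it through.** **Inputs from the documents.** SDs 1.2 and 1.0, r = 0.5, n = 85, change 0.4, two-sided alpha 0.05 (section E). Number of classes K = 4 × 2 = 8 to 6 × 2 = 12 (section D).

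**Input assumed.** ICC of the A1C change, 0.01-0.05. The documents give none.

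**Step 1: reproduce the plan's figure.**
- SD of change = √(1.2² + 1.0² − 2 × 0.5 × 1.2 × 1.0) = √1.24 = 1.114
- SE = 1.114/√85 = 0.1208
- Power = Φ(0.4/0.1208 − 1.96) = 0.912; a paired t-test on 84 df gives 0.906

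The stated 90% is arithmetically right under independence.

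**Step 2: add clustering.** Mean class size m = 85/K, which is 7.08 for 12 classes and 10.62 for 8.
- DEFF = 1 + (m − 1) × ICC
- True SE / independence SE = √DEFF
- Actual type I error of the unadjusted test = 2 × [1 − Φ(1.96/√DEFF)]
- Power of a correctly sized test, z reference = Φ(0.4/(0.1208 × √DEFF) − 1.96)

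| K | ICC | DEFF | SE ratio | Type I error | Power for 0.4 |
|---|---|---|---|---|---|
| 12 | 0.01 | 1.061 | 1.03 | 0.057 | 0.895 |
| 12 | 0.02 | 1.122 | 1.06 | 0.064 | 0.878 |
| 12 | 0.05 | 1.304 | 1.14 | 0.086 | 0.826 |
| 8 | 0.01 | 1.096 | 1.05 | 0.061 | 0.886 |
| 8 | 0.02 | 1.192 | 1.09 | 0.073 | 0.858 |
| 8 | 0.05 | 1.481 | 1.22 | 0.107 | 0.777 |

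The change detectable with 90% power, (1.96 + 1.28) × 0.1208 × √DEFF, rises from 0.39 under independence to 0.45 (12 classes) or 0.48 (8 classes) at ICC 0.05.

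**Step 3: separate the few-classes penalty.** A t reference on K − 1 df gives power 0.833 (12 classes) or 0.774 (8 classes) at ICC 0.01, and 0.752 or 0.648 at ICC 0.05. It gives only 0.85 or 0.81 at ICC 0, so much of that drop comes from the degrees of freedom and not from clustering.

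**Step 4: vary the other inputs.**
- Pilot-sized change of 0.8 (9.3% to 8.5%, section C): power is at least 0.99 throughout the assumed ICC range with 8 or 12 classes, even on K − 1 df.
- r = 0.7: SD of change = √(2.44 − 1.68) = 0.872. Power for 0.4 at ICC 0.05 is 0.96 (12 classes) or 0.94 (8 classes). The type I error formula does not contain r, so the error rates in the table are unchanged.
- Class count: planned sizes of 10-20 would give 100/20 = 5 to 100/10 = 10 classes. With 5 classes, m = 85/5 = 17; at ICC 0.05, DEFF = 1 + 16 × 0.05 = 1.80 and the SE ratio is √1.80 = 1.34. Fewer, larger classes make the problem worse.

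**The case against.** The strongest reply is that the ICC is unknown and may be close to zero. Section G says the materials can be read as a script, and an instructor's manual standardises content. Attendance is by Zoom or in person, with make-up classes and recordings. All of this could dilute class-specific effects. Nor do the documents assign a facilitator to each class; the same staff could teach all of them. This stands as a reason to state the problem conditionally and to treat it as minor at ICC 0.01 or below. It does not justify an implicit ICC of exactly zero.

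A second reply is that the plan has slack. It expects r above 0.5, and it aims for 100 completers. With 100 analysed at r = 0.5 and ICC 0.02, DEFF is 1 + (100/12 − 1) × 0.02 = 1.147 or 1 + (100/8 − 1) × 0.02 = 1.23, and power is 0.92 or 0.90. This stands for power. Neither a higher r nor more participants in the same classes corrects the error rate.

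Two stronger readings are tempting, and the documents support neither. A reader might infer that the 90% power claim is simply wrong. It reproduces from its own inputs, and whether it is too high depends on an ICC nobody has stated. A reader might also infer that Aim 2 suffers more, because "The first convening will occur after 1 education cycle has been completed for both an English- and Spanish-speaking cohort" and the period before the convening would then rest on about two classes. But the plan states no test or standard error for Aim 2 that could be wrong, and a class-level analysis is barely estimable from two classes.

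**Conclusion.** The point holds in conditional form. Group delivery, a pooled primary contrast and the absence of any class term are all in the documents. The direction is certain for any positive class ICC of the A1C change; the size is not known. Over an assumed ICC of 0.01-0.05, with 85 analysed in 8-12 classes of roughly equal size, the unadjusted test runs at a two-sided 0.057-0.107 instead of 0.05. Power for a 0.4 change is between 0.90 and 0.78 on the z reference.

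The case rests on valid error rates and interval width, not on a trial likely to miss its target, since power stays high for a change as large as the pilot's. The randomised RT-CGM comparison is largely unaffected.

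**What to change.** In the Aim 1 model, and in the Aim 3 models that estimate the curriculum effect, account for class (language by cycle) in the pooled change. Use either one class-level random effect on change or class-clustered standard errors, with a small-sample correction such as Kenward-Roger for the mixed model. Name in advance the fallback to be used if the class variance is estimated at zero. Restate the pre-post power in section E over a declared ICC range and an explicit number of classes.

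No new data are needed: language and cycle are known for each participant, and attendance is already tracked. The costs are somewhat wider intervals, a less favourable stated power, and a class variance imprecisely estimated from few classes. The last is why one class term is preferable to several, and why the fallback has to be written down beforehand.

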Revisions to the study protocol that enhance access and engagement will be implemented for the remainder of the study period, and indices of engagement (% of eligible participants who enroll, % of education sessions attended, % of participants who complete all study procedures, % adherence to CGM use) will be measured prior to and after the changes implemented consequent to the stakeholder convening. Key stakeholders will be convened again in years 2 and 3 of the project. These meetings also will focus on barriers to sustaining the intervention, particularly with regard to the availability of essential resources (CGM devices; CDEs, health educations, PN, and other personnel; infrastructure to support remote education sessions, etc.) and therefore will be key for the design of future interventions.

Key stakeholders:

The advisory board will be chaired by [name], MD, Director of the UW Medicine Diabetes Institute LatinX Diabetes Clinic. Other members will include PN and members of Ventanillas de Salud (a local chapter with the Mexican consulate that works to combat health disparities). In addition, Spanish-speaking diabetes educators, primary care providers, and a quality improvement officer from Sea Mar will be included in the board. Ten participants from the first two cohorts (5 from each cohort of participants (with the goal to include 2 participants who withdrew from the intervention). We will ask

the first 3 participants who enrolled and completed greater than 70% of the sessions to be on the board. We will also ask the first 2 participants who stopped going to the sessions to be on the advisory board. If they decline we will continue to ask the next participant enrolled until we have 3 participants who have engaged in the educational sessions and 2 participants who stopped attending the sessions.

We hope to improve the diabetes classes and discuss any challenges people may be having with participating in the diabetes classes, and challenges with telemedicine sessions. We will ask questions either in a group setting or 1:1 tele-health interview about living with diabetes and any barriers/difficulties they are experiencing. Interviews will last approximately 50-60 minutes and will be recorded in order to ensure all answers are transcribed and then collated in a de-identified manner for QI for the program

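### Aim 2's primary attendance outcome is limited to study completers, a group left undefined, so the before/after comparison conditions on the retention that the stakeholder revisions aim to change

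*Combined protocol and SAP*

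**What the plan says.** Section E, Data Analysis Plan, Aim 2, sets the primary outcome as the "difference in % of DSMES education sessions attended for participants who complete the study before and after the stakeholder convening". Its next sentence adds further engagement endpoints, among them the percentage "of participants who complete all study visits". It names no model, effect size or power for this aim.

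Section O (Advisory Board) gives the purpose of the convening: "Key stakeholders will meet specifically to address barriers to entering and completing the education intervention". It then lists the engagement indices again, including the percentage "of education sessions attended, % of participants who complete all study procedures", and says that they "will be measured prior to and after the changes implemented consequent to the stakeholder convening". That list attaches no completer restriction to attendance, and it places the dividing line at the implemented changes rather than at the meeting.

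No section defines completing the study. The opening statement of Aim 2 mentions completers and non-completers without saying who they are, and section D sets a goal of 100 completed out of at most 120 enrolled. Section G classes a participant as a dropout after 4 consecutive or 8 total missed classes, but does not link that rule to completion. It also keeps everyone in follow-up data collection whatever their attendance.

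**The concern.** Whether someone completes is decided after the revisions have had their chance to act, and improving completion is one of their stated purposes. An attendance comparison among completers therefore compares two groups selected by a process that the revisions may have altered. Participants who leave, and who probably attended little, are absent from both sides. If the revisions work by keeping such people in class, much of the gain lies outside the primary outcome.

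The outcome also cannot be programmed as written. The analyst would have to choose what completion means and whether the split falls at the convening or at the changes. A cohort being taught between those two dates would count as after under section E and as before under section O.

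At stake is the answer to Aim 2, whether the stakeholder process improved engagement. Aim 1 is not touched.

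**Working it through.** **No figure to reproduce.** The plan gives no attendance rate, SD or power for Aim 2. What follows is an illustration, and every attendance rate in it is assumed.

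**Inputs**
- Attrition before the revisions: 15%, borrowed from Sample Size Estimation (100 reduced to 85), where it serves Aim 1. Section D's 100 completed of at most 120 enrolled implies up to 20/120 = 16.7%, which is similar.
- Attrition after: *a*, assumed 5%, 10% or unchanged at 15%. Newly retained share *k* = 0.15 − *a*.
- Attendance of completers before: 80% (assumed). Rise among those who would have completed anyway: *x*.
- Attendance of newly retained people: *R* (assumed). Attendance of lost people: *D*, assumed 10% to 60% and the same in both periods.

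**Formulas**, in percentage points
- All randomised: 0.85*x* + *k*(*R* − *D*).
- Completers only: [0.85(80 + *x*) + *kR*]/(1 − *a*) − 80. Because 1 − *a* = 0.85 + *k*, this equals [0.85*x* + *k*(*R* − 80)]/(1 − *a*).

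**Results**

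| Case | Completers only | All randomised |
|---|---|---|
| *x* = 0, *R* = 80, *a* = 5% | (68 + 8)/0.95 − 80 = 0.0 | 0.10 × (80 − 60) = +2.0 to 0.10 × (80 − 10) = +7.0 |
| *x* = 0, *R* = 80, *a* = 10% | (68 + 4)/0.90 − 80 = 0.0 | 0.05 × 20 = +1.0 to 0.05 × 70 = +3.5 |
| *x* = 0, *R* = 70, *a* = 5% | (68 + 7)/0.95 − 80 = −1.1 | 0.10 × 10 = +1.0 to 0.10 × 60 = +6.0 |
| *x* = 5, *R* = 80, *a* = 5%, *D* = 60 | (72.25 + 8)/0.95 − 80 = +4.5 | 4.25 + 2.0 = +6.25 |
| *x* = 5, *a* = 15% (no change) | 72.25/0.85 − 80 = +5.0 | 0.85 × 5 = +4.25 |

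**Reading the table**
- A gain that comes wholly through retention, with newly retained people attending like the others, is missed.
- With the others unchanged, any *R* below 80 makes the completers-only difference negative, since it equals *k*(*R* − 80)/(1 − *a*).
- A mixed gain is attenuated rather than missed.
- With attrition unchanged, a gain among completers is overstated: *x* against 0.85*x*.

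**If completion meant not being a dropout under section G**, a completer would have missed fewer than 8 of 12 classes and so attended at least 5/12 = 41.7%. The outcome would then partly define its own population. No section says that this rule applies.

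**The case against.** **Class dropouts stay in the study.** Section G keeps all participants in follow-up data collection. If completion means attending study visits, someone who leaves class but keeps the visits is still a completer, and that low attendance stays in the outcome. This stands, and it makes the problem smaller under that definition. It does not help those who leave the study altogether, and the plan does not say that this is the definition.

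**The phrase may only sort people by when they finished.** That is a fair reading of the grammar. People who never finish still fall in neither group.

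**Retention is a separate endpoint.** True, and a retention gain would show there. It would not correct the primary outcome.

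**The illustration is built to give zero.** It is: 0.0 follows from *x* = 0 and *R* = 80, and other inputs give attenuation, a negative value or overstatement. The direction is therefore not fixed.

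**Sampling error is larger.** Assume 25 participants before and 75 after (section O expects 20 to 30 before) and an attendance SD of 15 to 30 points. The 95% half-width is 1.96 × SD × √(1/25 + 1/75) = 0.453 × SD, or 6.8 to 13.6 points, so the illustrated 1 to 7 points lies at or within the noise. That limits what Aim 2 can show, but it is no reason to leave the population undefined.

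**Stronger readings that the documents do not support**
- A reader might infer that completion means the 24-week visit, so that nobody has completed when the board first meets. Section O sets the meeting "after approximately 20-25% of participants have completed the 12-week intervention" and adds: "The first convening will occur after 1 education cycle has been completed for both an English- and Spanish-speaking cohort". Neither passage says how soon the meeting follows, and both tie completion to the education period, not to the last visit.
- A reader might take "the first 3 participants who enrolled and completed greater than 70% of the sessions" as a definition of completion. It is only a rule for choosing board members.
- A reader might see a flat contradiction between sections E and O. Section O names no population, so the two are unaligned rather than contradictory.

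**Conclusion.** The point holds in limited form. The Aim 2 primary outcome rests on an undefined completer group, leaves people who never complete out of both periods, and so conditions on something the revisions are meant to change. It also differs from section O in population and in where the periods divide.

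It would go too far to say that the plan will understate the effect. Size and direction depend on the definition of completion and on attendance rates that the plan does not give. Under the assumed rates, a retention-driven gain of +2.0 to +7.0 points (attrition 15% to 5%) or +1.0 to +3.5 points (15% to 10%) appears as 0.0 among completers; with attrition unchanged, a completer gain of *x* is reported where the all-randomised gain is 0.85*x*. The effect is smaller if completion means study visits. This is a worthwhile, inexpensive improvement confined to Aim 2.

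**What to change.** - In section E, define the Aim 2 primary outcome as the percentage of the 12 sessions attended among all randomised participants, with unattended sessions counted as not attended. State whether make-up classes and viewed recordings count as attendance, since section G offers both.
- Group participants by whether their class cohort started before or after the first convening's revisions were implemented, and report any straddling cohort separately. Say how revisions from the later convenings in years 2 and 3 are handled.
- Align section O with section E on population and dividing line.
- Keep completers-only attendance as a descriptive secondary, with completion defined.

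**Cost:** a few sentences, with no added participants or visits. Section G already tracks attendance through the Zoom chat, and the gift cards in section T for 4 and for 8 or more sessions require a count per participant. Because pseudonyms are allowed and classes may be held in person, the attendance record should be tied to the study number in both settings. The one drawback is that average attendance will look lower than it would among completers.
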